5.4. Exclusion criteria for RCT

1. Participant is active (150 or more minutes of moderate-vigorous intensity activity per week)
2. Major health interventions such as surgery, radiation, or chemotherapy within the past 6 months (adjuvant treatments such as tamoxifen are okay)
3. Stroke, hip fracture, hip or knee replacement, or spinal surgery in the past 6 months
4. Report a history of orthopedic complications that would prevent optimal participation in the physical activities prescribed (e.g., heel spurs, severe arthritis)
5. Current evidence of cancer
6. Self-reported smoker
7. Participant reports psychological issues that would interfere with study completion. Examples will be provided to illustrate potential psychological issues, such as dementia or schizophrenia.
8. Participant reports hospitalization within the past year due to psychiatric problem(s)
9. Clinical judgment concerning safety
10. Currently participating in an organized commercial or research exercise program
11. Another member of the household is a participant or staff member on this trial
12. Current use of a wearable activity monitor

5.5. Rationale for inclusion/exclusion criteria

We will not recruit individuals who cannot speak English due to the need to understand the app, which is in English.

Participants will likely be moderate risk as designated by the American College of Sports Medicine, and thus we want to be conservative in our eligibility criteria. If participants endorse any question on the PAR-Q+, they will automatically be ineligible due to unacceptably high risk unless they produce a note from their physician clearing them for participation.

We will focus specifically on cancer survivors who are at least six months post major treatment to ensure that complications do not impact the safety of exercises.

Other exclusion criteria exist to exclude variables that could potentially affect participation in the trial. We will also exclude those with a BMI indicating that they are underweight as we are interested in adults of normal weight, overweight, and obese status. Underweight may indicate other health problems that could compromise participant safety. We will include obese adults up to a BMI of 40, but those over 40 are likely to be substantially different from our target population and will require independent study in the future.

Other health exclusions are for the purposes of safety and unbiased data (e.g., substance use disorder).

No exclusion criteria or quotas will be related to race, ethnicity, or gender.

5.6. Recruitment strategies

Participants will be recruited using several methods:

1. In-person recruitment at UTMB and MD Anderson clinics
2. Phone and email screening of eligible patients at MD Anderson clinics
3. Referrals from practitioners at both institutions
4. Flyers and brochures available in treatment and waiting areas of both institutions, community clinics in Galveston and surrounding areas.
5. Mailed letters and emails to members of research and cancer registries at both institutions
6. Targeted Facebook advertisements
7. Emails to local organization listservs (each institution, local cancer support groups, etc.)
8. Presentations at local cancer and wellness events
9. As necessary, newspaper and radio advertisement

Specifically, recruitment of MD Anderson patients may occur by flyer, in-person, by email, or by phone. Study staff at MD Anderson will review upcoming patient appointments in the clinic via EPIC. Participants who look to be eligible will be called over the phone to explain to them the study procedures and see if they are interested in participating. This procedure is regularly used successfully by our collaborators at MD Anderson. Whereas at UTMB we must obtain practitioner permission to approach patients, all MD Anderson patients have provided consent to be approached by research-related phone calls. Reciprocal approval of all screening materials, protocols, etc by the MD Anderson IRB will be obtained prior to any recruitment. Participants will also be screened at that time to ensure that they are eligible to participate in the study. If the patient is interested and eligible, UTMB study staff will call to set up an appointment for informed consent, baseline assessment, and randomization/study orientation. MD Anderson staff will assist with this pre-screening but will not be involved in intervention or assessment procedures. MD Anderson clinics will be a recruitment site only, not an intervention site (i.e., UTMB consent forms will be used, MD Anderson personnel will not have access to any non-screening-related study data, etc.).

5.7. Randomization

A random number generator will be used to create a list of group assignments by ID number. Sheets containing group assignments (intervention or comparison group) will be placed in envelopes that are labeled with the corresponding ID number. The envelopes will be opaque, and foil will be placed inside to ensure that the randomizer cannot see inside. Carbon paper will also be included to provide an audit trail. ID numbers will be assigned in the order participants arrive to their randomization visit. Upon opening the envelope, the staff member undertaking the randomization will sign and write the date on the envelope. The inner paper that lists the group assignment, with the ID, signature, and date written on it via carbon paper, will be kept in the participant's file.

5.8. Blinding

Because of the nature of this behavioral study, participants and interventionists cannot be blinded to their group assignment.

5.9. Participant withdrawal

Participants may withdraw from the study at any time. Withdrawal prior to the end of the study will not affect the safety of participants. The consent form lists the following potential reasons that participants may be removed by the investigators:

- The researchers believe that participation in the research is no longer safe for you.
- The researchers believe that other treatment may be more helpful.
- The sponsor stops the research for the safety of the participants.
- The sponsor cancels the research.
- You are unable to keep appointments or to follow the researcher's instructions.

5.10. Premature termination or suspension of study

There is no reason to believe that the proposed intervention would produce increased risk as compared to standard self-monitoring. Because anticipated risks and benefits to individual participants are small, we do not anticipate early termination of the study due to excessive risk or differences in anticipated benefits.

5.11. Participant remuneration

For the initial formative study, participants ($n = 20$) will receive \$50 for their participation. Participants in this study do not get to keep any of the study materials. For the RCT, participants will receive \$50 incentive for attending assessments (\$25 at 12 weeks and \$25 at 24 weeks) and will be able to keep the activity monitors and other supplies provided. Parking will also be provided.

6. INTERVENTIONS

6.1. Description of the active control group intervention

This group will receive only a wearable activity monitor, app, and workbook. We will use Fitbit. The workbook will contain a weekly calendar with prompts to write in that week's goal and whether each daily goal was achieved. Basic pen supplies will be provided for writing in the workbook. At orientation, instruction will be provided on the use of the materials, and participants will set long-term (24 weeks) goals and their goals for the first week. Goals are based on estimates of appropriate step counts for older adults with chronic illness.³³ Goals will be negotiated with each participant, based on their baseline totals. The suggested progression will be from 2 days per week at 8,000 steps (week 1) to 5 days per week at 8,000 or more steps (from week 6 on). Negotiated goals are critical in an autonomy-promoting study, to ensure that participants do not feel controlled. The standard protocol will include daily reminders to log progress in the workbook negotiated with participants and expected to occur via automated phone reminders set to occur every day at a time they choose). After their final assessment, participants in this condition will receive the additional supplies given to the narrative visualization intervention participants.

In summary, the active control group will receive an activity monitor, mobile app, and a workbook. This workbook will include simple diary-like calendar pages. Participants will be instructed to enter their step count into these calendars every night.

6.2. Description of the narrative visualization intervention

This intervention builds upon the standard intervention by expanding the workbook and providing art supplies and an instant camera for more detailed reflection activities. The orientation meeting will include extended instructions on using the additional materials as well as tips and examples for creating narrative visualizations.

The workbook will include two pages for each calendar day. One page will include a blank chart for drawing their interpretation of their step chart for the day. Ample space will be provided for writing, drawing, and placing stickers or photos at various points in the chart to represent things that happened that day. The workbooks will have sufficient pages for 12 weeks of entries. **Figure C.1.** shows an example of narrative visualization, though participants will be encouraged to be creative in how they annotate their charts.

In this very simple example, a standard step chart (taken from the Nike Fuelband app) was annotated with emojis to show what was going on that day. Without the annotations, the user would know that she met her step goal, but would not know why PA dropped off late in the day. Here, it is clear that a planned running bout and a trip to the beach to play with the wharf cats were the causes of the early activity. The lack of activity at the end of the day coincided with attending a party, drinking too much, and getting sick. This narrative clearly offers a starting point for reflection: perhaps in the future, more pleasant trips to do fun things could be planned, and the participant could limit drinking at parties. These visuals also relate the steps to personal values, such as spending time outdoors and socializing. Visual triggers provide a foundation for figuring out how to interpret PA data and what to do to change behavior in the context of one's values and identity.

Table C.1 shows examples of daily and weekly reflection questions that can be answered with a combination of text and visuals (please note that these prompts may change based on the results of the Aim 1 interviews). We will also include additional one-time prompts to provide context for these reflections. For example, we will ask participants in their first week to take photos that represent how they feel about themselves and photos that represent their values, following the procedures of a published photo values clarification activity.²⁰

Table 1. Reflection prompts

Timing	Prompt
Daily	How were you active today? Why do you think you were (or were not) active today? What impacted your decisions about activity today?
Weekly	Looking back, do you see any patterns in your activity? How can you take this knowledge and use it to be more active next week? How do you feel about your progress this week? Do you feel closer to your goals?

potentially explanatory pictures).

In summary, the narrative visualization group will receive an activity monitor, a mobile app, a workbook, and an art supply kit. This art supply kit will include an instant camera, writing materials, stickers, photo paper, and photo corners for pasting photos into the workbook. The workbook will differ from that of the active control group. This workbook will contain a values clarification exercise, which will involve participants taking 10 photos over a period of about one week. These photos will be of things the participant values and will be used as a jumping-off point for connecting personal values to reasons to be physically active. The daily pages for entering steps will also be more elaborate than those of the active control group. These pages will include a blank graph on which participants will draw their step graph and add text, drawing, and sticker annotations that explain what they were doing at different times. There will also be space for including photos of interesting things seen on walks (and sufficient photo paper will be provided for daily photos). Daily and weekly reflection questions will encourage participants to think about why they were active each day and how their behavior changed over time.

Figure C.1. Example narrative visualization

Art supplies will include adequate film for one photo per day for 12 weeks, decorative tape for pasting photos into the workbook, writing materials, and stickers (e.g., emojis or other

Element	Active control	Narrative visualization
Activity monitor	x	x
Mobile app	x	x
Reminders to log steps nightly	x	x
Art supply kit (camera, writing materials, stickers, photo corners, photo paper)		x
Workbook pages:		
Daily diary calendar pages	x	

Values clarification activity		x
Daily blank graphs		x
Daily reflection questions		x
Weekly reflection questions		x

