6.3. Administration of intervention

The interventions are primarily self-guided, with minimal personal attention from interventionists. Participant contact with interventionists will occur at the orientation visit only.

Daily texts/emails that serve to remind participants to complete their workbook page that day will be generic and not considered personal intervention.

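### The documents conflict on whether the narrative workbook keeps the written weekly goal prompt and the daily goal-achieved log

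*Combined protocol and SAP*

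**What the plan says.** Three places describe the narrative arm as the standard intervention with something added. Aim 2 (section 3.1) sets self-monitoring plus narrative visualization against standard self-monitoring. Section 1 says the narrative group also gets further workbook material. Section 6.2 says: "This intervention builds upon the standard intervention by expanding the workbook".

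The goal elements appear on the control side only. Section 6.1 says of the control workbook: "The workbook will contain a weekly calendar with prompts to write in that week's goal and whether each daily goal was achieved". Section 1 likewise attributes writing and logging weekly goals to the self-regulation group.

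The closing summary of 6.2 states "The workbook will differ from that of the active control group". It lists a values exercise, daily step pages with a blank graph, photo space, and daily and weekly reflection questions. The element table that follows marks "Daily diary calendar pages" for the active control and leaves the narrative column blank.

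Several things are explicitly common to both arms. The table marks the monitor, the app and "Reminders to log steps nightly" in both columns. Section 6.2 keeps step entry: "The daily pages for entering steps will also be more elaborate than those of the active control group". Section 8.3 lists a goal-setting activity at orientation under each arm. Section 6.3 adds: "Participant contact with interventionists will occur at the orientation visit only".

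**The concern.** Section 1 names goal setting, alongside self-monitoring and feedback, as a technique behind the short-term success of standard interventions. The plan itself therefore treats it as an active component. If one arm has a written weekly goal and a daily record of meeting it, and the other does not, randomised groups differ by more than the narrative content.

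Two results would be affected. One is steps at 12 weeks. The other is integrated regulation, where section 10.2 requires at least a small between-arm effect before the programme moves on. Either result, favourable or not, would reflect narrative content added and written goal work removed, with no way to separate them. The planned adherence data would not show this directly: the workbook indicators in section 3.2 have no separate count of goals written or goals met.

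**Working it through.** No arithmetic decides this point. The plan's one design figure, 80% power at f = 0.45 with 40 participants, is not an input. It does reproduce: with noncentrality 0.45² × 40 = 8.1, 1 and 36 degrees of freedom and an assumed two-sided alpha of 0.05, power is 0.79.

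The check is a comparison of the texts, element by element.

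| Element | Control arm | Narrative arm |
|---|---|---|
| Monitor, app, nightly reminders | Yes (6.2 table) | Yes (6.2 table) |
| Daily step entry | Yes (6.1) | Yes, on fuller pages (6.2) |
| Goal setting at orientation | Yes (8.3) | Yes (8.3) |
| Diary calendar pages | Marked (6.2 table) | Blank (6.2 table) |
| Written weekly goal prompt | Yes (1, 6.1) | Not described; implied if the arm is additive |
| Daily goal-achieved record | Yes (6.1) | Not described; implied if the arm is additive |
| Values activity, graphs, reflection questions | Blank (6.2 table) | Marked (6.2 table) |

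1. **Additive reading.** If the narrative workbook is the standard one expanded, the goal prompt and log carry over and the contrast is as Aim 2 states it.
2. **Itemised reading.** The table marks shared items in both columns, so a blank cell carries information. Section 6.1 describes the control workbook first as a weekly calendar with goal prompts and then, in its closing summary, as diary-like calendar pages. If these are the same pages, the blank cell takes the goal prompts with it.
3. **What would remain under the itemised reading.** Section 6.1 has orientation set the 24-week goal and the first week's goal, and suggests a progression up to week 6. Under 6.3, orientation is the only contact with interventionists. For weeks 2 to 12 (12 − 1 = 11 of the 12 intervention weeks), the narrative arm would have no described page for a new weekly goal or for recording whether it was met. The example weekly reflection questions ask about progress, closeness to goals and how to be more active the following week, but none asks for a goal to be written or its achievement logged.

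The two readings lead to different printed workbooks, and nothing in the documents chooses between them.

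**The case against.** The strongest reply is that removal is nowhere stated. The table has no row for goal prompts. Its blank cell concerns pages that the 6.1 summary describes as the place to enter step counts, and 6.2 replaces those with fuller step pages. Equating them with the weekly calendar is an inference. The narrative workbook is also not fully itemised: 6.2 allots two pages to each day but at that point describes one, and it presents the reflection prompts as examples that may change after Aim 1. The week 1 goal and the progression are themselves described only in the control section, so anyone who carries those over to the narrative arm should be ready to carry over the goal prompt too. All of this stands, and it means that omission is not established.

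It is also fair that the stakes are limited. The primary outcomes are feasibility and acceptability, analysed descriptively; significance will not be interpreted; and the quantitative results mainly serve to shape a later trial. The proceed criterion in 10.2 is nevertheless a between-arm comparison, so the content of each arm still matters.

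A reader might infer that the narrative arm loses self-monitoring, so that the Aim 2 contrast fails outright. The documents do not support that: the monitor, app, reminders, daily step entry and orientation goal setting are all shared. A reader might also want to put a size on the distortion. Nothing in the documents says what written goal logging is worth for steps or for integrated regulation, so no figure can be given.

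**Conclusion.** The point holds as an inconsistency with a conditional consequence. Sections 1, 6.1 and 6.2 do not agree on whether the narrative workbook retains the written weekly goal prompt and the daily goal-achieved log. The side-by-side table leans towards omission; the additive wording leans the other way.

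If the elements are absent, the arms differ by a removal as well as an addition, and differences in steps and integrated regulation could not be attributed to narrative visualization alone. That conclusion assumes that the workbooks follow the table, that the calendar pages in the table are the ones carrying the goal prompts, and that no unlisted narrative page serves the same purpose. Confidence is moderate for that reason. The matter should be settled because the affected comparison feeds the decision to proceed.

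**What to change.** Reconcile section 1, section 6.1, and the text and element table of 6.2. Print the same weekly goal prompt and the same daily goal-met line in both workbooks, and add a table row, *weekly goal and daily goal-achieved log*, marked in both columns.

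If the narrative workbook is meant to replace the goal pages, say so. Reword Aim 2 and 6.2 as a comparison of two packages, and limit the conclusion to that.

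The cost is small. If the pages are already shared, it is one table row and a clarifying sentence. If they were left out by oversight, it is one prompt per week and one line per day in a workbook the study already produces, with slightly more writing for the narrative arm. If the omission is deliberate, it is a wording amendment. Randomization and sample size are unchanged in every case.

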6.3. Administration of intervention

The interventions are primarily self-guided, with minimal personal attention from interventionists. Participant contact with interventionists will occur at the orientation visit only.

Daily texts/emails that serve to remind participants to complete their workbook page that day will be generic and not considered personal intervention.

6.4. Procedures for training interventionists and monitoring intervention fidelity

Interventionists will be trained by the Principal Investigator to conduct the orientation visit. Intervention fidelity is itself an outcome of this study and as such is detailed in the measures and statistical analysis sections of this protocol.

6.5. Assessment of participant compliance with study intervention

Participant compliance is an outcome of this study and as such is detailed in the measures and statistical analysis sections of this protocol.

7. STUDY SCHEDULE – AIM 1 FORMATIVE STUDY

7.1. Screening

We have collaborated with oncologists at various clinics to expand our effort in recruitment. A HIPAA waiver request form has been completed. With the oncologist's approval, we will pre-screen patients via medical records for eligibility. The oncologists will refer their patients. We will not approach patients unless we have oncologist's and patient's permission.

Research staff will use the Aim 1 screening guide, either in person or by phone, to determine eligibility in the study. Should the participant be found eligible, the staff member will schedule an appointment for informed consent and enrollment.

7.2. Enrollment and provision of materials

Research staff will conduct the informed consent interview. Once the interview is complete and participants have asked any questions they may have, the participant and staff member will each sign two copies of the consent form. One copy will be provided to the participant and the other kept for study records.

The staff member will then use the Aim 1 visit 1 checklist to go through study procedures for this visit. S/he will provide participants with materials (activity monitor, workbook, camera, film, writing materials, photo corners, stickers) and go over instructions for their use. At the conclusion of the visit, the staff member will schedule an appointment for the return visit after approximately one week.

- Obtain and document consent from participant on study consent form
- Administer Aim 1 Visit 1 checklist/interview guide
- Provide and document the following materials:
 - Activity monitor
 - Instant camera
 - Workbook (binder with pre-printed instruction pages for 7 days + values activity + troubleshooting guide)
 - Writing materials
 - Stickers
 - Film for camera
 - Photo corners for pasting photos in workbook
 - Bag to hold materials
- Set up activity monitor app on the participants' mobile device & daily reminder

